12.2. Serious Adverse Events

A serious adverse event (SAE) is defined as any adverse event that results in any of the following outcomes:

- Death
- Life-threatening experience
- Required or prolonged inpatient hospitalization
- Persistent or significant disability/incapacity
- Congenital anomaly/birth defects

Life-threatening experience: Any adverse event that places the patient, in the view of the reporter, at immediate risk of death from the adverse event as it occurred, i.e., does not include an adverse event that had it occurred in a more severe form, might have caused death.

Persistent or significant disability/incapacity: The adverse event that resulted in a substantial disruption of a person's ability to conduct normal life functions.

Important medical events based upon appropriate medical judgment, that may jeopardize the patient or subject and may require medical or surgical intervention to prevent one of the outcomes listed above: Adverse events that may not result in death, be life-threatening, or require hospitalization may be considered a serious adverse event when, based upon appropriate medical judgment, they

may jeopardize the patient or subject and may require medical or surgical intervention to prevent one of the outcomes listed above.

The investigator will be asked to assess the severity of the adverse drug/biologic experience using the following categories: mild, moderate and severe. This assessment is subjective and the investigator should use medical judgment to compare the reported adverse event to similar type events observed in clinical practice. Below are listed guidelines for severity assessment:

- **Mild:** Symptom(s) barely noticeable to the subject/patient or does not make the subject/patient uncomfortable. The adverse event does not influence performance or functioning. Prescription drugs are not ordinarily needed for relief of symptom(s).
- **Moderate:** Symptom(s) of a sufficient severity to make the subject/patient uncomfortable. Performance of daily activities is influenced. Treatment of symptom(s) may be needed.
- **Severe:** Symptom(s) of a sufficient severity to cause the subject/patient severe discomfort. Severity may cause cessation of treatment with the study drug. Treatment for symptom(s) may be given.

12.3. Adverse Event and Serious Adverse Event Reporting

The necessity and time requirements for reporting of SAEs are as follows:

All SAEs and subject terminations will be reported to the Principal Investigator within 24 hours.

[figure not shown]
All SAEs will be reported to the Principal Investigator and to the RDCRN through the DMCC Adverse Event Data Management System within 24 hours of the investigator's first knowledge of the event, even if the experience does not appear to be related to the study drug. This also includes those events that are unexpected/unanticipated or is considered life-threatening/disabling or results in the death of a subject.

For all SAEs, a detailed written description that includes copies of relevant patient records, autopsy reports, and other documents will be collected.

Additionally, the IRB must be notified in writing of any events falling into these categories. It is the responsibility of the investigator to notify the IRB within **24 hours** if the event is unanticipated or is considered life-threatening/ disabling or results in the death of a subject. All other reportable SAEs must be reported within **5 working days** (of learning of the event).

All AEs and SAEs will be noted on the CRF, with a full description including the nature, date and time of onset and resolution, determination of seriousness, severity, corrective treatment, outcome, and relationship to study drug.

Flowchart for Adverse Event Reporting

12.4. Institutional Review Board

The study will be approved by the institutional review board (IRB) at each respective study site. All investigators must obtain IRB approval.

12.5. Food and Drug Administration Investigational New Drug Application

A new IND has been filed to the FDA [1,354]. The investigator and all study personnel will conduct the study according to FDA requirements.

12.6. Data and Safety Monitoring Board (DSMB)

The DSMB will review the research protocol, informed consent documents and plans for data safety and monitoring, evaluate the progress of the trial, including periodic assessments of data quality and timeliness, number of subjects screened, number enrolled, number dropped with reason for discontinuation, interim and cumulative data from all study sites, adverse events and serious adverse events, performance of the trial sites, and other factors that can affect study outcome. The establishment of a DSMB was recommended because of the inherent risks, the multicenter nature of the trial, and the significant financial

interest involved in this research. At the initial DSMB meeting, the DSMB will approve the study protocol and consider data elements to be included in the periodic reports to the DSMB. See DSMB Charter. During the initial meeting, the DSMB will also develop the Standard Operating Procedure of the DSMB. This SOP will be forwarded to the LABiomed IRB and GCRC for review.

The DSMB will provide the Sponsor-Investigator with the minutes from the open sessions of the DSMB meetings and summary report with any recommendations for future study conduct (continuation, modification or termination of the study). The Sponsor-Investigator will provide copies of the minutes, reports and recommendations to each site's co-investigators, the LABiomed IRB, and the GCRC Advisory Committee.

This study protocol will also be reviewed and approved by the National Institutes of Health (NIH). This is an interventional study that meets the federal definition of moderate risk.

The Principal Investigator has primary oversight of this clinical trial. The Principal Investigator and the Steering Committee will review accrual patterns, adverse events, data quality, and protocol compliance on an annual basis.

12.7. Local Reporting

The investigator will prepare a periodic report to include target, interval and cumulative data in a tabular format for subjects enrolled at Harbor-UCLA Medical Center and for the entire study as follows:

- Number of subjects screened
- Number of subjects enrolled
- Number of subjects not qualified for enrollment based on screening with reason for screen failure
- Dropout number with reason for dropout and stage of study at dropout.
- Completion number
- All adverse events with severity and attribution. During the period between the treatments and the follow-up period, the rates of adverse event related to underlying disease and routine illnesses (URI, headaches, muscle aches, etc.) and traumatic injuries are not expected to be different than usual and will not be reported as unexpected AEs but will be tracked and reported as AEs for the DSMB reports.
- For all serious adverse events (SAEs) and all unexpected adverse events (UAEs), the clinical summary will also be provided in a cumulative fashion. For SAEs and UAEs, IRB and GCRC policy on adverse event reporting will be followed.

To ensure subject confidentiality, all subjects will be identified by a numerical identifier only.

The primary monitor for this study is the DSMB. The data and safety monitoring board will be comprised of three persons: a statistician, a neurologist, and a pediatrician geneticist. All DSMB members will be external to the Los Angeles Biomedical Research Institute at Harbor-UCLA Medical Center, and shall have no financial interest in the institute, Aldurazyme, or in the companies that manufacture and distribute Aldurazyme (i.e. BioMarin Pharmaceutical, Inc. and Genzyme Corp.).

A separate DSMB charter will be drafted and approved by all board members prior to reviewing any data. The members of this DSMB should not have substantial conflicts of interest and have no substantive financial ties to the applicant or to the proposed research and will be required to submit an affidavit to these effects.

The board will convene every four months at the inception, during, and at the end of the study period. Due to the small number of subjects and the relatively small number of visits, every 4 months is recommended to allow review of relevant data. An emergency meeting of the DSMB may be called at any time by the DSMB Chairperson or the Sponsor-Investigator should question of subject safety arise.

12.8. RDCRN Adverse Event Data Management System (AEDMS)

Upon entry of a serious adverse event by a site investigator, the DMCC created Adverse Event Data Management System (AEDMS) will immediately notify the Principal Investigator. The Principal Investigator is responsible for notifying NINDS staff.

Serious adverse events: The site investigator determines causality (definitely not related, probably not related, possibly related, probably related, definitely related) of the adverse event. The DSMB will also review the SAE incident report.

The DSMB may request further information if necessary and possibly suggest changes to the protocol or consent form to the NINDS as a consequence of adverse events. A back-up notification system is in place so that any delays in review by the DSMB chair beyond a specified period of time are forwarded to a secondary reviewer. The Adverse Event Data Management System (AEDAMS) maintains audit trails and stores data (and data updated) and communication related to any adverse event in the study.

Non-serious expected adverse events Except those listed above as immediately reportable, non-serious expected adverse events that are reported to or observed by the investigator or a member of his/her research team will be

submitted to the DMCC in a timely fashion (within 20 working days). The events will be presented in tabular form and given to the DSMB on a quarterly basis or as requested. Local site investigators are also required to fulfill all reporting requirements of their local institutions.

The DMCC will post aggregate reports of all adverse events (serious/not serious and expected, unexpected) for site investigators and IRBs.

All reported adverse events will be classified using the current version of the Common Terminology Criteria for Adverse Events (CTCAE) developed and maintained by CTEP at National Cancer Institute.

12.9. Unanticipated Problem Reporting

The Office for Human Research Protections (OHRP) considers unanticipated problems involving risks to subjects or others to include, in general, any incident, experience, or outcome that meets **all** of the following criteria:

unexpected in terms of nature, severity, or frequency given (a) the research procedures that are described in the protocol-related documents, such as the IRB-approved research protocol and informed consent document; and (b) the characteristics of the subject population being studied;

related or possibly related to participation in the research ("possibly related" means there is a reasonable possibility that the incident, experience, or outcome may have been caused by the procedures involved in the research); and

suggests that the research places subjects or others at a greater risk of harm (including physical, psychological, economic, or social harm) than was previously known or recognized.

Per the definition, only a subset of adverse events would be characterized as unanticipated problems. There are other types of incidents, experiences, and outcomes that are not considered adverse events, but are characterized as unanticipated problems (e.g., breach of confidentiality or other incidents involving social or economic harm).

Incidents or events that meet the OHRP criteria for unanticipated problems are to be reported to the IRB, per local institutional reporting requirements. Local institutional reporting requirements to IRBs, any GCRC oversight committee and the FDA, if appropriate, remain the responsibility of the treating physician and the Study Chair.

12.10. Discontinuation Guidelines

The participation of all study subjects will be halted pending review by the NIH, DSMB and IRB for the following reasons:

- WHO Grade 3 toxicity (such as a seizure or meningitis) is experienced by 2 or more subjects
- Death or WHO Grade 4 toxicity is experienced by 1 or more subjects

If one of the above conditions are met, the study will be placed on hold (no new enrollment, and a halt to all study procedures on enrolled subjects), and the PI will notify the NIH, IRB and DSMB within 24 hours.

This study may be also suspended or closed if:

- Accrual has been met
- The study objectives have been met
- The Study Chair / Study Investigators believe it is not safe for the study to continue
- The RDCRN DSMB suspends or closes the trial
- The NIH suspends or closes the trial
- The FDA suspends or closes the trial

13. Data Quality Assurance

All required data will be recorded on the CRF. All missing data will be explained. If a space is blank because the item was not done, the item will be marked "ND." If the item is unknown, item will be marked "UNK." If the item is not applicable to the individual case, the space will be marked with a "NA." If the item is not available, it will be marked with "NAV." All entries will be recorded in black ink. If an entry error has been made, a single straight line will be drawn through the wrong entry and the correct data will be entered above it and initialed and dated. ERRORS MAY NOT BE ERASED AND WHITEOUT MAY NOT BE USED.

The CRFs will be reviewed manually at the study site for completeness. All data will be entered into a study database for analysis and reporting. Any data captured electronically (e.g., laboratory data) will be electronically transferred to the database. Upon completion of data entry, the database will receive a quality assurance (QA) check to ensure acceptable accuracy and completeness.

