The study will be conducted at the Los Angeles Biomedical Research Institute at Harbor-UCLA (LAB-HUCLA), Children's Hospital Oakland Research Institute

(CHORI) and the University of Minnesota (UMN). Additional study sites may be added as subjects are identified. Specific details are below:

- Recruitment: Subjects will be recruited from participants in the MIRC-002 study at LAB-HUCLA and CHORI.
- Procedures: Procedures will be performed at LAB-HUCLA, CHORI, and additional study sites that are added as subjects are recruited to the study. The addition of any new study site will be contingent upon approval by their local institutional review board (IRB), and the IRB at LAB-HUCLA. Neuropsychological testing will be performed at UMN.
- Regulations: The IRBs at CHORI and UMN will oversee the research at these respective sites, with LAB-HUCLA the primary site responsible.

4. Resources Available to Conduct the Human Research

Since subjects will be recruited from among participants enrolled in the pilot (MIRC-002) study:

- All participants are accessible for recruitment
- 67% are anticipated to be enrolled in the proposed study
- Study staff have previously been involved with participants and their families through the pilot study, so are familiar with local culture and attitudes toward clinical research.

Time requirement for the Principal Investigator to conduct and complete the proposed study within the agreed trial period is projected to be 8 hours per week.

Site study staff at the LAB-HUCLA include six members: two co-Primary Investigators, two pharmacists, one Study Coordinator, and one laboratory staff. Study staff at the CHORI site include three members: one site PI, one pharmacist and one study coordinator. Study staff at the UMN include two members: one site PI and one study coordinator. All study staff have completed appropriate training regarding protection of human research subjects, Good Clinical Practices, and HIPAA, and have previously participated in other clinical research trials.

Inpatient study treatments are conducted at the hospital in an area designated for clinical research and study evaluations are completed in separate outpatient clinical research facilities. Principal Investigators have hospital privileges at their respective sites and non-study staff resources are available at each hospital should study participants require medical or psychological support as a result of an anticipated consequence of the research study.

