6.4. Study Timelines

The duration of each subject's participation in the study is expected to be five years. We anticipate enrolling these subjects over a 4-year period. The estimated date of completion of the study is 10 years following the onset of the study.

7. Procedures Involved in the Human Research

This study is a five-year open-label, prospective trial in 6 MPS I subjects age six years or greater who have completed a 24-month open label study (MIRC-002). Potentially eligible subjects who (or, if appropriate whose parents or guardians) have provided signed, written informed consent will first participate in a baseline screening phase. This will occur at least six months after subjects have completed the MIRC002 pilot study. During baseline screening, the subjects will receive the baseline evaluations outlined below, and their eligibility will be determined. Every three months, subjects will receive intrathecal recombinant human α-L-iduronidase (IT rhIDU) approved as Aldurazyme® [laronidase] for the treatment of cognitive impairment in patients with mucopolysaccharidosis I (MPS I). Neuropsychological testing and MRI will be performed at baseline and at one year intervals. Safety will be monitored continuously throughout the subject's study participation through recording all adverse events (AEs) and periodically performing clinical and laboratory evaluations.

Study subjects will receive intrathecal enzyme therapy only during the study; intrathecal enzyme therapy will not be administered at the end of the five-year period. If further intrathecal enzyme is desired, the subject may enroll in further intrathecal research if another study is available.

To assure that subjects enrolling in the trial have maximum access to alternative therapy, subjects will be asked to receive counseling regarding other available appropriate medical and surgical alternatives prior to enrollment in this trial.

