7.2. Schedule of Study Evaluations

After obtaining informed consent, the investigator will conduct the study as outlined in the following sections. Table 1 summarizes the nature of the assessments and treatments and their timelines. Refer to Study Operations Manual for guidelines regarding test assessments and procedures for handling/shipment of all central laboratory samples.

Table 1 Schedule of study assessments and treatments

Month Number	Baseline	Visit 1/Odd Numbered Visits	Visit 2/Even Numbered Visits	End Study
Neuropsychological testing	X		yearly	
MRI of brain	X		yearly	
Clinical tests				
History and Physical examination	X	X	X	X
Neurologic examination	X	X	X	X
Photography and video (optional)	X	X	X	X
Six-minute walk test	X	X	X	X
Subjective response of clinical symptoms	X	X	X	X
FIM scoring	X	X	X	X

Laboratory tests (CSF)				
Protein, glucose, cell count		X	X	
GAG levels		X	X	
Anti-rhIDU antibody		X	X	
CSF iduronidase assay		X	X	
Laboratory tests (blood)				
Anti-rhIDU antibody	X	X	X	X
CBC, Chem panel 20, Coagulation studies	X	X	X	X
Neurophysiologic test				
CSF flow study	X			
Investigator Global Assessment				
	X	X	X	X
Treatments				
Intrathecal rhIDU		X	X	

Visits occur at three-month intervals starting from Visit One. There may be a variable period between Baseline/Screening and Visit One from five days to three months. If the period between Baseline/Screening and Visit One is less than one week, then all of the other assessments do not need to be repeated for Visit One.

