9.3.3.2. History and physical examination

At each visit, each subject will be classified as experiencing an adverse event if clinically significant worsening from baseline medical status, as described in Section 7.8.1.1, has occurred. The frequency and percent of subjects experiencing such an event will be tabulated for each visit.

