9.3.3.3. Standard CBC and Chemistry Measurements

At each visit, each subject will be classified as experiencing an adverse event if there is clinically significant CBC or chemistry panel worsening from baseline, as described in Section 7.8.1.2.4. The frequency and percent of subjects experiencing such an event will be tabulated for each visit.

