12.1. Adverse Events

Subjects in this study will be closely monitored during the enzyme administration and for one hour afterward with frequent (every 15 minutes) vital signs and continuous pulse oximetry. The subject will be able to contact the investigator or other appropriate personnel to report adverse events occurring later. These will be treated with appropriate medical care where applicable. Adverse events that are unanticipated will be reported within 10 working days to the institutional review board.

An adverse event (AE) is any undesirable physical, psychological or behavioral effect (an unfavorable and unintended sign, symptom or disease) experienced by a subject during their participation in an investigational study whether or not product-related. This includes any untoward signs or symptoms experienced by the subject from the time of signing of the informed consent until completion of the study. Adverse events may include, but are not limited to:

- Subjective or objective symptoms spontaneously offered by the patient or subject and/or observed by the investigator or medical staff.
- Laboratory abnormalities of clinical significance.
- Disease signs, symptoms and/or laboratory abnormalities already existing prior to the use of the study medication are not considered adverse events after treatment unless they reoccur after the subject has recovered from the pre-existing condition or they represent an exacerbation in intensity or frequency.

All reportable AEs will be assigned a relationship to the study drug by the principal investigator. A drug-related AE is an event with a plausible time relationship to drug intake that cannot be explained by the disease or other drugs.

Any AEs experienced by the subject, from the time of signing the Informed Consent Form through the completion of study participation, will be reported as described (see Section 11.3) and recorded on the CRF. If AEs are present when the patient completes study participation, the subject will be re-evaluated within two weeks of completion and the results of this re-evaluation will be recorded on the CRF. If AEs are not resolved, additional follow-up will be performed as appropriate. All reportable AEs must be reported to the RDCRN within **20 working days** of the notification of the event or of the site becoming aware of the event.

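### The section 12.10 toxicity hold stops all study procedures, not only dosing, so as worded it also suspends scheduled safety checks and conflicts with the monitoring commitment in sections 7 and 7.8

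*Combined protocol and SAP*

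**What the plan says.** Section 12.10 sets two triggers: Grade 3 toxicity in at least two subjects, or one death or Grade 4 event. When either is met, "The participation of all study subjects will be halted pending review by the NIH, DSMB and IRB", and "the study will be placed on hold (no new enrollment, and a halt to all study procedures on enrolled subjects". The section states no duration and no exception for safety assessments.

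On the schedule, section 7.2 says "Visits occur at three-month intervals starting from Visit One". Table 1 places the history and physical, neurologic examination, CBC, chemistry, coagulation tests and serum antibody at the same visits as the intrathecal dose.

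On monitoring, the opening of section 7 and section 7.8 both commit to continuous safety monitoring while a subject participates, by recording adverse events and by clinical and laboratory evaluations at intervals. Section 12.1 defines the adverse event window as running "from the time of signing of the informed consent until completion of the study".

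**The concern.** A hold should stop what may be causing harm: new enrolment, the drug, and the lumbar puncture and sedation that go with it. It should not stop observation of people already exposed. The wording of 12.10 does not separate the two. Because dose and safety checks share a visit, a site that follows the sentence literally would cancel the examinations and blood draws along with the injection. That would happen just after a serious event, in subjects who received the same intrathecal drug, and while the NIH, DSMB and IRB are deciding what to do. A site that relies on section 7.8 would keep the checks going. Two sites could therefore act differently under the same protocol.

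**Working it through.** **Step 1: are the safety checks study procedures?** The heading of section 7.7 is Other Study Procedures. Under it sit the history and physical (7.7.3.1), neurologic examination (7.7.3.2), serum antibody (7.7.4.2.1), CBC and chemistry (7.7.4.2.2) and coagulation (7.7.4.2.3). The word *other* implies that section 7.6, the dosing procedure, is a study procedure too. Section 7.6 includes the inpatient neuro checks and vital signs after injection and the outpatient examination the day after discharge. Read literally, 12.10 halts all of these.

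**Step 2: does another clause keep them running?**

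| Section | What it provides | Does it cover a subject on hold with no reported event? |
|---|---|---|
| 7, 7.8 | Clinical and laboratory evaluations at intervals during participation | In direct conflict with 12.10, which halts participation; precedence not stated |
| 12.1 | Open event window, subject may make contact, care given, unresolved events followed | Event recording yes; scheduled tests no |
| 9.3.3.4 | Other events recorded from one injection to the next | Event recording yes; scheduled tests no |
| 14.1, 14.2 | Follow-up after discontinuation or withdrawal, tied mainly to adverse events | No; these concern subjects leaving the study |
| 12.3, 12.7, 12.8 | 24-hour SAE reporting, emergency DSMB meeting, DSMB information requests | These act mainly on what is reported or already collected |

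Sections 9.3.3.2 and 9.3.3.3 classify examination and laboratory events by visit ("At each visit, each subject will be classified as experiencing an adverse event if clinically significant worsening from baseline medical status"; "At each visit, each subject will be classified as experiencing an adverse event if there is clinically significant CBC or chemistry panel worsening"). These are tabulation rules, but such events do need an examination or a blood draw to be found (7.7.3.1, 7.8.1.2.2).

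**Step 3: size, given that a hold occurs.** The plan gives no figure to reproduce.

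Inputs from the protocol:
- Visits every 3 months (7.2).
- At most six subjects (9.2).
- Entry: "We anticipate enrolling these subjects over a 4-year period", with five years on study each (6.4).
- Uptake: "67% are anticipated to be enrolled in the proposed study" (section 4), and 0.67 × 6 ≈ 4.

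Assumed: hold length h of 1, 3 or 4 months (4 is the routine DSMB interval in 12.7), visits spread evenly over time, subjects entering at equal spacing, and a trigger equally likely at any time in the triggering subject's participation.

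Visits missed or postponed = k × h/3, where k is the number of other subjects on study.

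Mean k with staggered entry = (n − 1) × (5 − mean pairwise entry difference)/5.
- n = 6: spacing 4/5 = 0.8 years; mean difference 0.8 × 7/3 = 1.867; k = 5 × 3.133/5 = 3.13.
- n = 4: spacing 4/3 = 1.333 years; mean difference 1.333 × 5/3 = 2.222; k = 3 × 2.778/5 = 1.67.

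| Others on study | h = 1 | h = 3 | h = 4 |
|---|---|---|---|
| Staggered, 6 enrolled (k = 3.13) | 1.04 | 3.13 | 4.18 |
| Staggered, 4 enrolled (k = 1.67) | 0.56 | 1.67 | 2.22 |
| Ceiling, one triggering subject of 6 (k = 5) | 1.67 | 5.00 | 6.67 |
| Ceiling, one triggering subject of 4 (k = 3) | 1.00 | 3.00 | 4.00 |
| Ceiling, two triggering subjects of 6 (k = 4) | 1.33 | 4.00 | 5.33 |
| Ceiling, two triggering subjects of 4 (k = 2) | 0.67 | 2.00 | 2.67 |

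The ceilings need every subject on study at once. With entry spread over 4 years and 5 years each, that lasts about 5 − 4 = 1 year.

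For one subject, the longest gap between safety visits is 3 + h, so 4, 6 or 7 months, if the visit is made up when the hold ends.

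**The case against.** The strongest reply is that section 7.8 already covers subjects who have reported nothing, and that a temporary halt pending review does not complete anyone's participation. On that reading the evaluations continue. This stands in part: it makes the problem a conflict between two clauses and not a settled suspension. It does not remove the problem, because 12.10 is the specific rule for a hold and says that participation is halted.

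A reader might also infer that exposed subjects would go unmonitored, or lose tests that would show the same harm before symptoms. The documents support neither.
- Event recording, contact with the investigator and care continue under 12.1 and 9.3.3.4.
- The Grade 3 examples in 12.10 are seizure and meningitis. Section 15.2 places the canine seizures immediately after treatment, with none between treatments. Nothing shows that a CBC or chemistry panel months after a dose would anticipate such events.
- Antibody titers go for analysis only every six months (7.8.2.4.2), so a short hold costs little timely warning.
- CSF cell count and protein, the tests nearest to meningeal inflammation, need a lumbar puncture. A sensible hold would stop that as well.

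The neurologic examination is the check whose loss is hardest to dismiss.

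A full stop is also a conservative default that the reviewing bodies can change: 12.10 requires notice to them within 24 hours, 12.7 allows an emergency DSMB meeting at any time, and 12.6 lets the DSMB recommend modification. All of that stands and keeps the likely effect small, but none of it tells a site what to do on the first day of a hold.

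**Conclusion.** The point holds as a defect of wording with minor consequences. Section 12.10 literally halts the scheduled safety examinations and blood tests of dosed subjects, and the post-injection monitoring and next-day visit of anyone just treated. Sections 7 and 7.8 say otherwise, and neither is given precedence. The loss falls mainly on scheduled checks in subjects with no reported event.

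The size is conditional on a hold, whose probability is not estimated. At one month with staggered enrolment it is about 0.6 to 1.0 visits across all other subjects, and a short hold may touch no visit at all. At four months, an assumed upper case, it is about 2.2 to 4.2 visits. These figures rest on the assumed hold lengths, even entry and evenly spread visits.

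The sponsor may have meant to stop dosing only. The DSMB Charter, its operating procedure and the Study Operations Manual were not available for this review, nor was some of the text in section 15. Any of them might already limit the hold.

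**What to change.** Replace the definition of the hold in 12.10 with wording such as:

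> The hold stops new enrolment and intrathecal rhIDU dosing, with its lumbar punctures and sedation. Adverse event follow-up, scheduled non-invasive safety examinations, safety blood tests and any post-injection monitoring already under way continue unless the DSMB, IRB or NIH directs otherwise.

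The opening sentence of 12.10, which halts participation, should be aligned so that it no longer contradicts 7.8. The triggers and analyses do not change. The cost is about two sentences, using staff and visits already planned. The one downside is that subjects keep attending safety visits during a hold. If the charter or operations manual already limits the hold in this way, 12.10 need only be made to match.
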